5.6 Dose Modification

At the discretion of the study physician, the vaccine injection may be delayed because of a current or recent febrile illness. Low-grade fever itself (temperature ≤ 100.4) and mild upper respiratory infection are not generally contraindications to vaccination.

Participants who develop anaphylactic reactions following the first injection will permanently discontinue Gardasil 9.

5.7 Adherence/Compliance

5.7.1 Participants are considered compliant for statistical analysis if they have received all doses of the vaccine.

5.7.2 The compliance will be measured by the number of vaccines administered.

6. PHARMACEUTICAL INFORMATION

6.1 GARDASIL 9 (IND exempt by FDA 8/12/15)

This clinical study investigating the chemopreventive efficacy of recombinant human papillomavirus (HPV) nonavalent vaccine, Gardasil 9, has been deemed IND exempt per FDA letter received on 8/12/15. Gardasil 9 is indicated for prevention of cervical, vulvar, vaginal, and anal cancers caused by HPV types 16, 18, 31, 33, 45, 52 and 58, and for the prevention of genital warts caused by HPV types 6 or 11 in females 9–26 years of age and males 9–15 years of age. Gardasil 9 adds protection against five additional HPV types—31, 33, 45, 52, and 58—which cause approximately 20% of cervical cancers and are not covered by previous FDA-approved HPV vaccines.

Gardasil 9 is manufactured by Merck Sharp and Dohme Corp., a subsidiary of Merck & Co., Inc. (Whitehouse Station, New Jersey). It is supplied in 0.5 mL single-dose vials as a sterile suspension for intramuscular administration. Each 0.5 mL dose contains approximately 30 µg HPV Type 6 L1 protein, 40 µg HPV Type 11 L1 protein, 60 µg HPV Type 16 L1 protein, 40 µg HPV Type 18 L1 protein, 20 µg HPV Type 31 L1 protein, 20 µg HPV Type 33 L1 protein, 20 µg HPV Type 45 L1 protein, 20 µg HPV Type 52 L1 protein, and 20 µg HPV Type 58 L1 protein. Each 0.5 mL dose of the vaccine also contains approximately 500 µg aluminum (provided as amorphous aluminum hydroxyphosphate sulfate [AAHS]), 9.56 mg sodium chloride, 0.78 mg L-histidine, 50 µg polysorbate 80, 35 µg sodium borate, <7 µg yeast protein, and water for injection. The product does not contain a preservative or antibiotics. After thorough agitation, Gardasil 9 is a white cloudy liquid.

6.2 Reported Adverse Events and Potential Risks

The manufacturer evaluated the safety of Gardasil 9 in six clinical studies that included 13,234 individuals who received at least one dose and had safety follow-up. The vaccine was administered on the day of enrollment, with subsequent doses administered approximately two and six months thereafter. Safety was evaluated using vaccination report card (VRC)-aided surveillance for 14 days after each injection of Gardasil 9. The individuals who were monitored using VRC-aided surveillance included 8,022 women 16–26 years of age and 5,212 girls and boys 9–15 years of age (3,436 girls and 1,776 boys) at enrollment.

Injection site reactions (pain, swelling, and erythema) and oral temperature were solicited using VRC-aided surveillance for five days after each injection of Gardasil 9 during the clinical studies. The rates of injection site pain were approximately equal across the three reporting time periods; the rates of injection site swelling and injection site erythema increased following each successive dose of Gardasil 9. Unsolicited injection site and systemic adverse reactions were assessed as vaccine-related by the investigator. Few individuals discontinued study participation due to adverse experiences after receiving the vaccine.

The most common ($\geq 10\%$) local and systemic adverse reactions in females 16–26 years of age who received Gardasil 9 were injection site pain (89.9%), injection site swelling (40.0%), injection site erythema (34.0%), and headache (14.6%). The most common ($\geq 10\%$) local and systemic reactions in girls 9–15 years of age who received Gardasil 9 were injection site pain (89.3%), injection site swelling (47.8%), injection site erythema (34.1%), and headache (11.4%). The most common ($\geq 10\%$) local and systemic reactions in boys aged 9–15 years who received Gardasil 9 were injection site pain (71.5%), injection site swelling (26.9%), and injection site erythema (24.9%).

Serious adverse events (SAEs) were collected throughout the entire study period (range one to 48 months post-last dose) for the six integrated clinical studies with Gardasil 9. Of the 13,236 individuals who were administered Gardasil 9 and had safety follow-up, 305 reported an SAE, representing 2.3% of the population. Five reported at least one SAE that was determined to be vaccine-related: pyrexia, allergy to vaccine, asthmatic crisis, headache, and tonsillitis. There were no vaccine-related deaths among individuals administered Gardasil 9 in the clinical studies.

In all of the clinical trials with Gardasil 9, subjects were evaluated for new medical conditions potentially indicative of a systemic autoimmune disorder. In total, 2.4% (321/13,234) of Gardasil 9 recipients reported new medical conditions potentially indicative of systemic autoimmune disorders, which were similar to rates reported following Gardasil, AAHS control, or saline placebo in historical clinical trials.

The safety of Gardasil 9 when administered concomitantly with Menactra (Meningococcal [Groups A, C, Y and W-135] Polysaccharide Diphtheria Toxoid Conjugate Vaccine) and Adacel (Tetanus Toxoid, Reduced Diphtheria Toxoid and Acellular Pertussis Vaccine Adsorbed [Tdap]) was evaluated in a randomized study of 1,241 boys (n = 620) and girls (n = 621) with a mean age of 12.2 years. Of the 1,237 boys and girls vaccinated, 1,220 had safety follow-up for injection site adverse reactions. The rates of injection site adverse reactions were similar between the concomitant group and nonconcomitant group (vaccination with Gardasil 9 separated from vaccination with Menactra and Adacel by one month) with the exception of an increased rate of swelling reported at the injection site for Gardasil 9 in the concomitant group (14.4%) compared to the non-concomitant group (9.4%). The majority of injection site swelling adverse reactions were reported as mild to moderate in intensity.

Reproductive studies performed in female rats at a dose approximately 240 times the human dose on a mg/kg basis revealed no evidence of impaired female fertility or harm to the fetus due to Gardasil 9. There are, however, no adequate and well-controlled studies in pregnant women. Because animal reproduction studies are not always predictive of human responses, Gardasil 9 should be used during pregnancy only if clearly needed. It is not known whether Gardasil 9 is excreted in human milk. Because many drugs are excreted in human milk, caution should be exercised when Gardasil 9 is administered to a nursing woman.

The safety and effectiveness of Gardasil 9 have not been established in pediatric patients below nine years of age.

Immunosuppressive therapies, including irradiation, antimetabolites, alkylating agents, cytotoxic drugs, and corticosteroids (used in greater than physiologic doses), may reduce the immune responses to Gardasil 9.

6.3 Availability

Gardasil 9 will be purchased by each study site according to the institutional practice.

6.4 Agent Distribution

The study site may not dispense study agent until a complete regulatory package, including IRB approval, is provided to DCP and a drug shipment authorization email is received by the site.

6.5 Agent Accountability

Careful records of the inventory and disposition of all agents will be maintained by the pharmacist or designee at each site according to the institutional policy.

6.6 Packaging and Labeling

Not applicable.

6.7 Storage

Gardasil 9 is supplied in single-dose vials and should be stored in a secure location protected from light at temperatures between 2°C and 8°C (36°F and 46°F).

6.8 Registration/Randomization

Participants will be considered registered on the date they sign the assent form and their legal representative(s) sign the approved informed consent document with a member of the study staff. This study does not involve randomization.

6.9 Blinding and Unblinding Methods

Not applicable.

6.10 Agent Destruction/Disposal

Institutional policy will be followed for agent destruction/disposable.

7. CLINICAL EVALUATIONS AND PROCEDURES

7.1 Schedule of Events

Evaluation/ Procedure	Prestudy Evaluation	Baseline Visit ¹	Months 1-6	Month 6 Visit ⁴	Months 7-12	Month 12 Visit ⁴	Months 13-18	Month 18 Visit ⁴	Months 19-24	Month 24 Visit ⁴	Months 24-30	Month 30 Visit ⁴	Follow-up ²
Informed Consent/Assent	X												
Parental/Household Questionnaire	X												
Assess Eligibility	X												
Medical History	X												
Age of Menarche, if applicable	X	X		X		X		X		X		X	
Urine Pregnancy Test ⁵	X	X								X		X ⁷	
Baseline signs and symptoms	X												
Vital Signs	X	X ⁶								X		X ⁷	
Weight, Height	X	X ⁶				X				X			
Concomitant Medications	X	X		X		X		X		X		X	
Blood Collection		X		X		X		X		X		X	
Priming Vaccine Injection		X											
Booster Injection										X		X ⁷	
Adverse Events		X	X	X	X	X	X	X	X	X	X	X	X
Telephone/email/text Contact ³			X		X		X		X		X		X

¹Baseline visit should occur within 90 days of enrollment and can be combined with the prestudy evaluation.

²Participants will be followed for 2 weeks after completing the last Gardasil 9 injection.

³Participants and their legal representative(s) will be contacted once a month to remind them to refrain from non-study HPV vaccination during the study period and also within two weeks prior to each study visit to remind them of their upcoming visit.

⁴Study visits will occur +/- 2 weeks of the scheduled times unless significant scheduling problems arise.

⁵For girls who have started their periods.

⁶Not required, if the baseline visit occurs within one month of the prestudy evaluation

⁷The booster injection is optional at the Month 30 visit. Urine pregnancy test and vital signs are not required at this visit for participants who do not receive the 3rd injection.

7.2 Baseline Testing/Prestudy Evaluation

Participants will undergo a pre-study screening evaluation. The legal representative(s) of the participants will be required to sign the informed consent form and medical records release form. Participants will be asked to sign the assent form. Participants and their legal representative(s) will be interviewed for past medical history (including age of menarche) and concomitant medication use. Participants will be assessed for height, weight, and vital signs (temperature, pulse, and blood pressure). Participants will be evaluated for baseline signs and symptoms. Urine pregnancy test will be performed on participants who have started menstrual periods. The legal representative(s) will complete a questionnaire to collect information on the participant's parental education attainment and household income.

Eligible participants and their legal representative(s) will return to the clinic for a baseline visit. This visit may be combined with the prestudy screening evaluation visit. If the baseline visit occurs more than 30 days from the screening visit, participants will be reassessed for weight and vital signs. Adverse events and concomitant medications will be reviewed and age at menarche and urine pregnancy test, if applicable, will be reassessed at the baseline visit unless it occurs on the same day as the screening visit. If the participant is pregnant, she will be considered off-study and not undergo additional study procedures, including vaccination. A blood sample will be collected from the participants and serum separated and stored at -80°C. Participants will be offered topical anesthetic cream to be applied to the blood collection site prior to the collection. Following the blood collection, participants will receive the priming injection of Gardasil 9. Participants should be seated or lying down during vaccine administration. Participants will be required to sit or lie down for 15 minutes after the vaccine injection to help prevent fainting and injuries caused by falls and be observed in the clinic for at least 15 minutes. Topical anesthetic cream may be distributed to participants to apply at home prior to study visits requiring blood draws. This may be done either by giving the cream to the participant's parent/guardian while in the clinic or by mailing the cream to the participant's address.

7.3 Evaluation During Study

Participants and legal representatives will be instructed to record adverse events for two weeks following each injection which will then be mailed back to the study office in a pre-stamped and addressed envelope.

Participants and their legal representatives will return to the clinic at 6, 12, 18, 24, and 30 months after the priming injection of Gardasil 9. These study visits will occur +/- 2 weeks of the scheduled times unless significant scheduling problems arise.

For the months 6, 12, and 18 visits, participants will be assessed for adverse events, concomitant medications, menarche, if applicable. Weight and height will be assessed at the month 12 visit. A blood sample will be collected from the participants at each visit and serum separated and stored at -80°C. Similarly, participants will be offered topical anesthetic cream to be applied to the blood collection site prior to the collection.

For the months 24 and 30 visits, participants will be assessed for vital signs, adverse events, concomitant medications, and menarche and urine pregnancy test, if applicable. If the participant is pregnant, she will be considered off-study and not undergo additional study procedures, including vaccination. Weight and height will be assessed at the month 24 visit. A blood sample will be collected from the participants at each visit and serum separated and stored at -80°C. Similarly, participants will be offered topical anesthetic cream to be applied to the blood collection site prior to the collection. Following the blood collection at the month 24 visit participants will receive the booster injection of Gardasil 9. At the month 30 visit, a 3rd vaccine injection will be offered but is optional. Vital signs and urine pregnancy test are not

required for participants who do not receive the 3rd vaccine injection at the Month 30 visit. Participants should be seated or lying down during vaccine administration. Participants will be required to sit or lie down for 15 minutes after the vaccine injection to help prevent fainting and injuries caused by falls and be observed in the clinic for at least 15 minutes.

Participants and their legal representatives will be contacted monthly and within two weeks prior to each visit using their preferred method of contact to promote participant retention. Participants and their legal representatives will be reminded to refrain from non-study HPV vaccination during the study period. If a subject receives an HPV vaccine booster injection outside the context of the study, that subject will be taken off study. This information will be captured in the source document and on the Concomitant Medication CRF and a comment addressing this will be added to the Agent Interruption CRF.

7.4 Evaluation at Completion of Study

As described in section 7.3, the study ends at the month 30 visit.

7.5 Follow-up Period

Participants will keep a diary of any illness or injury for 2 weeks after the last Gardasil 9 injection and mail the diary back to the study office in a pre-stamped envelope provided by the study office.

In addition, participants and their legal representatives may be contacted in the future if they have consented to allow for the possibility of re-consenting for additional serologic testing after the trial is completed.

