1.2 Secondary Objectives

- To determine the persistence and stability of serologic GMT of HPV types 6/11/31/33/45/52/58 between 6, 12, 18, and 24 months after prime dose and prior to the administration of the second dose and
- To assess safety and reactogenicity to each vaccine dose.

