5.2 Gardasil 9 Administration

- Shake well before use.
- Administer the entire dose of Gardasil 9 (0.5 ml) intramuscularly in the deltoid region of the upper arm or in the higher anterolateral area of the thigh.
- Participants should be seated or lying down during administration.
- Participants should be observed in the clinic for at least 15 minutes following the administration of Gardasil 9.

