8.2 Secondary Endpoints

The secondary endpoints include

- Determination of the persistence and stability of serologic GMT of other carcinogenic HPV types 31/33/45/52/58 and non-carcinogenic HPV 6/11 between 6, 12, 18, and 24 months.
- Assessment of safety and reactogenicity to each vaccine dose.

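### Reactogenicity to each dose is a secondary endpoint, but the protocol specifies no solicited reactions, words the two-week home record in two ways, and does not commit to reporting by dose

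*Combined protocol and SAP*

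**What the plan says.** Section 1.2 sets the objective: "To assess safety and reactogenicity to each vaccine dose". Sections 8.2 and 13.5 repeat it. None of them lists component reactions, a day window or a reactogenicity scale.

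On collection, section 7.3 (and section 3 in the same terms) states: "Participants and legal representatives will be instructed to record adverse events for two weeks following each injection". The record is mailed back. Section 7.5 describes the record after the final dose as follows: "Participants will keep a diary of any illness or injury for 2 weeks after the last Gardasil 9 injection". The schedule of events in section 7.1 has no diary row.

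Other capture of adverse events is also described:
- Section 5.2: "Participants should be observed in the clinic for at least 15 minutes following the administration of Gardasil 9".
- Section 7.3: "For the months 6, 12, and 18 visits, participants will be assessed for adverse events", and likewise at months 24 and 30.
- Section 7.1: the adverse-event row is marked in every column from baseline to follow-up.
- Section 11.1: all adverse events go on the case report form, with onset date, attribution and CTCAE v4.0 grade.

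For analysis, section 13.7 plans descriptive frequencies of all adverse events with 95% confidence intervals. It does not say that these will be given by dose.

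Section 6.2 describes how the manufacturer's trials collected the same kind of data: "Injection site reactions (pain, swelling, and erythema) and oral temperature were solicited using VRC-aided surveillance for five days after each injection". This sat within a 14-day report card.

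**The concern.** Reactogenicity usually means the expected local and systemic reactions in the days after a dose. For this vaccine, section 6.2 shows that injection-site reactions are very common: pain in 89.3% of girls and 71.5% of boys aged 9–15, and swelling in 47.8% and 26.9%. A family asked an open question may not write down a sore or red arm, and the illness-or-injury wording of section 7.5 invites it even less plainly.

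What is at stake is the reading of a secondary safety endpoint. Section 6.2 reports that swelling and erythema rose with each successive dose in those trials, where doses were given at about 0, 2 and 6 months. Whether that also happens when the second dose comes 24 months after the first is a natural question for a per-dose objective. Open recording with no stated reaction list, and no commitment to tabulate by dose, is a weak basis for answering it.

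**Working it through.** **1. Does any other capture cover the days after a dose?**

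| Source | When it falls | Covers days 1–14? |
|---|---|---|
| Clinic observation (5.2) | First 15 minutes or more | No |
| Visit after dose 1 (7.3) | Month 6, six months later | By recall only |
| Visit after dose 2 (7.3) | Month 30, six months later | By recall only |
| Monthly contact (7.1, 7.3) | Between visits | Stated purpose is reminders and retention; adverse-event row also marked |
| Mailed home record (3, 7.3, 7.5) | Two weeks after the dose | Yes |

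The home record is the only participant record described for that window.

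**2. How does it compare with section 6.2?** The overall length is the same (two weeks against 14 days). The difference is that the section 6.2 trials solicited pain, swelling, erythema and oral temperature for five days. This protocol specifies no solicited item.

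**3. How sensitive would a rate be to incomplete recording?** The plan gives no precision figure for reactogenicity. As a check of method, the exact (Clopper-Pearson) interval reproduces the widths in section 13.4: the maximum 95% width is 0.2034 for n = 100 (stated 0.203) and 0.3280 for n = 39 (stated 0.328).

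Inputs: 143 girls and 57 boys (section 13.3), and reference rates p for ages 9–15 (section 6.2). The share c of reactions that an open diary captures is not in the documents; it is assumed, over the range 50% to 100%. The recorded count is x = round(n·p·c). The interval runs from the 2.5% quantile of Beta(x, n−x+1) to the 97.5% quantile of Beta(x+1, n−x).

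Example, girls' pain at c = 0.9: 143 × 0.893 × 0.9 = 114.9, so x = 115, which is 80.4% (73.0–86.6). The reference of 89.3% lies outside.

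| Item (reference) | c = 1.0 | c = 0.9 | c = 0.75 | c = 0.5 |
|---|---|---|---|---|
| Girls, pain (89.3%) | 89.5% (83.3–94.0) | 80.4% (73.0–86.6)* | 67.1% (58.8–74.8)* | 44.8% (36.4–53.3)* |
| Girls, swelling (47.8%) | 47.6% (39.1–56.1) | 43.4% (35.1–51.9) | 35.7% (27.8–44.1)* | 23.8% (17.1–31.6)* |
| Girls, erythema (34.1%) | 34.3% (26.5–42.7) | 30.8% (23.3–39.0) | 25.9% (18.9–33.9)* | 16.8% (11.1–23.9)* |
| Boys, pain (71.5%) | 71.9% (58.5–83.0) | 64.9% (51.1–77.1) | 54.4% (40.7–67.6)* | 35.1% (22.9–48.9)* |

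\* The interval excludes the reference rate.

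For girls' pain, the smallest count whose interval still reaches 89.3% is 120 of 143, or 83.9%. The corresponding capture is 0.839 / 0.893 = 0.94. The same threshold is about 83% for girls' swelling, 78% for girls' erythema and 83% for boys' pain. With the 100 girls expected to complete, the threshold for pain is about 93%.

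These figures show how strongly a rate depends on the collection method. They do not estimate a bias.

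**The case against.** The strongest reply has five parts.

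*The diary is not the only source.* A reader might infer that nothing else captures adverse events. The documents do not support that: sections 5.2, 7.1, 7.3 and 11.1 all provide for capture. What stands is narrower: no other participant record is described for the two weeks after a dose.

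*The diary form is not in the documents.* A reader might infer that it has no prompts, and that under-recording will occur. The text shows only that no prompts are specified, and no figure in it gives a capture share. The supportable word is may.

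*The two wordings probably describe one form.* A reader might infer that the question changes with dose, so that a difference between doses could be an artefact. Section 7.3 covers every injection, including the last, and section 7.5 describes the same two weeks and the same mail-back. Because the month 30 dose is optional, the last injection is the second for some children and the third for others, so a separate last-dose form would be awkward to run. This is inconsistent text, and two instruments are not shown.

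*Per-dose tables are feasible.* Onset dates are required (section 11.1.2) and injections are dated. If the same diary follows each dose and capture is equal, doses can be compared within the trial even with incomplete capture. This stands as to feasibility, but section 13.7 does not commit to it.

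*No comparison with section 6.2 is planned.* A reader might infer that the data cannot be read against section 6.2 at all. That goes too far: the overall window matches, and section 6.2 also mentions unsolicited reactions. But its injection-site rates were solicited and are not given by dose, so a comparison would not be like-for-like.

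**Conclusion.** The point holds in a limited form. A named secondary endpoint has no specified solicited collection, its home record is worded in two ways, and the planned analysis is not stated by dose. Common injection-site reactions may be under-recorded, and the rates would not be like-for-like with section 6.2.

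The size of any shortfall is unknown. The illustration rests on an assumed capture share and on the section 6.2 rates applying to these children. At full capture there is no shortfall; at 90% only girls' pain, among the four items tabulated, falls clear of its reference; at 75% all four do. The endpoint is descriptive, and the primary immunogenicity analysis is unaffected. The change is worth making because the better method is already described in section 6.2 and the mailed diary already exists.

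**What to change.** - Use one wording for the diary after every injection, in sections 3, 7.3 and 7.5.
- Add to the mailed diary a prompted daily checklist for the first five days after each injection: pain, swelling, erythema and oral temperature. Keep free text for other events to day 14, and state how the prompted items are graded.
- Add the diary to the schedule of events in section 7.1.
- In section 13.7, report the prompted items by dose and sex, with the number of diaries returned after each dose.

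**Cost:** a slightly longer form for families, a case report form page and an amendment, with no added visit. There is one real drawback. Sections 2.3 and 13.4 show that the protocol was amended after the study began, so some children may already have had a dose under the existing diary. A new checklist would change the instrument between their doses. Report results by diary version, and do not compare doses across versions.

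If the existing form already prompts for these items, it is enough to say so in the protocol, align the wording and report by dose.
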